Real-time EEG analysis: The EEG system will stream data in real-time to a dedicated computer. This computer will analyze the data in real time to identify brain states associated with strong or weak corticospinal tract recruitment (see above), or a random mixture of the two. When desired states are identified, either a single TMS pulse (see *Evaluation of state-targeting* accuracy) or the TST (see *TST assessment*) will be triggered. *Evaluation of state-targeting accuracy:* <= 150 single TMS pulses will be applied to the scalp at <= 120% of scalp RMT during EEG recordings.

Calculation of ISIs for TST assessment: The following stimulation procedures will be performed to calculate the ISIs for TST assessment.

- 1. <= 25 Single-pulse TMS to the scalp at <= 120% of scalp RMT
- 2. <= 25 Single-pulse PNS to the left wrist at <= 120% of M-max
- 3. <= 25 Single-pulse PNS to the left Erb's point at <= 120% of M-max

TST assessment: The TST will be applied according to an established protocol (Magistris et al. 1998) using consecutive application of TMS (<= 120% of scalp RMT), PNS at the left wrist (<= 120% of M-max), and PNS at the left Erb's point (<= 120% of M-max). The delays between each stimulus will be individualized based on each participants central and peripheral conduction times (see *Calculation of ISIs for TST assessment*). The TMS portion of the TST will be timed to occur during brain states reflecting strong corticospinal tract recruitment, weak corticospinal tract recruitment, or random brain states, using real-time EEG analysis. <= 50 TST applications will be performed per brain state condition.

Experiment 3

Design: within-subjects, single group Population: healthy adults (≥ 18 years old)

Conditions: At least 24 hours will elapse between sessions.

- 1. Active PCMS delivered during brain states reflecting strong corticospinal recruitment
- 2. Active PCMS delivered during brain states reflecting weak corticospinal recruitment
- 3. Active PCMS delivered during random brain states

- 4. Control PCMS delivered during brain states reflecting strong corticospinal recruitment
 - a. The order of conditions will be counterbalanced
 - b. Participants may complete one, two, three or four of the conditions

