Session frequency: Up to 4 sessions for <= 6 hours each. In the event of technical difficulties, <= 3 additional sessions may be requested, during which any combination of the procedures described below may be applied. Methodology:

EEG recordings: EEG will be recorded while participants rest quietly with their eyes open and during stimulation procedures. 64 EEG electrodes will be secured to the scalp using a swim-like cap and electrode gel. *EMG recordings:* EMG will be recorded from a maximum of 5 hand and wrist muscles while participants rest quietly and during stimulation procedures (see below, *Calculation of ISIs for PCMS* and *PCMS*). EMG will be recorded from <= 8 hand and wrist muscles.

Brain state discovery: <= 600 single TMS pulses will be applied to the scalp at <= 120% of scalp RMT during EEG recordings. These data will be used to identify brain states reflecting strong versus weak corticospinal tract recruitment using machine learning.

Real-time EEG analysis: The EEG system will stream data in real-time to a dedicated computer. This computer will analyze the data in real time to identify brain states associated with strong or weak corticospinal tract recruitment (see above). When states are identified, either a single TMS pulse (see *Evaluation of state-targeting* accuracy) or PCMS (see *PCMS*) will be triggered.

Evaluation of state-targeting accuracy: <= 150 single TMS pulses will be applied to the scalp at <=120% of scalp RMT during EEG recordings.

Calculation of ISIs for PCMS: The following stimulation procedures will be performed to calculate the ISIs for both control and active PCMS.

- 1. <= 25 Single TMS pulses to the scalp at <= 120% of scalp RMT
- 2. <= 25 Single PNS pulses to the left wrist at <= 120% of M-max

PCMS: PCMS will involve <= 150 pairs of scalp TMS and wrist PNS, applied repeatedly with >= 10 seconds between pairs. The TMS aspect of PCMS will be timed to occur during brain states reflecting strong corticospinal recruitment, brain states reflecting weak corticospinal recruitment, or random brain states, and the ISI between TMS and PNS will be based on individual peripheral and central conduction times (see *Calculation of ISIs for PCMS*).

Corticospinal excitability measurements: <= 25 single TMS pulses to the scalp at <= 120% RMT. Measurements will be taken immediately before PCMS and at 0, 20 and 40 minutes after PCMS.

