Spinal excitability measurements: <= 25 single PNS pulses to the left wrist at <= 120% of M-max. Measurements will be taken immediately before PCMS and at 0, 20 and 40 minutes after PCMS.

Voluntary motor output measurements: <= 5 maximum voluntary contractions of the FDI, each lasting <= 5 seconds. Measurements will be taken immediately before PCMS and at 0, 20 and 40 minutes after PCMS. Manual dexterity measurements. <= 5 attempts of the 9-hole peg test. Measurements will be taken immediately before PCMS and at 0, 20 and 40 minutes after PCMS.

5 Data Analysis

Describe the data analysis plan, including any statistical procedures or power analysis. To input text, click in the light grey area below.

Experiment 1:

- 1. Primary outcome: Amplitude of MEPs evoked during brain states reflecting strong, weak, and/or random corticospinal tract recruitment
 - a. This outcome will be evaluated using linear-mixed effects models (fixed effect of state, random effect of subject) with alpha equal to 0.05.

Experiment 2:

- 1. Primary outcome: amplitude of FDI muscle response after TST application during brain states reflecting strong, weak, and random corticospinal tract recruitment.
- 2. Secondary outcome: area under the curve of FDI muscle response after TST application during brain states reflecting strong, weak, and random corticospinal tract recruitment.
 - a. Both outcomes will be evaluated using linear mixed-effects models (fixed effect of state, random intercept of subject) with alpha equal to 0.05.

Experiment 3:

- 1. Primary outcomes: Maximum FDI force output, FDI activation (calculated using the root-mean-square of EMG signals obtained during FDI contractions)
- 2. Secondary outcome: Number of pegs placed per attempt at the 9-hole Pegboard test.
- 3. Exploratory outcomes: Amplitudes of MEPs produced by scalp TMS, amplitudes and persistence of Fwaves evoked by wrist PNS
 - All outcomes will be evaluated before and after PCMS. Outcomes will be analyzed using linearmixed effects models (fixed effects of condition and time point, random intercept of subject).
 Main effects will be evaluated using likelihood ratio tests, and p-values from post-hoc contrasts will be corrected for multiple comparisons. Alpha will be equal to 0.05.

STUDY ELEMENT IDENTIFICATION

6 Study Elements

Click on the check box (or double click and type an "X" if using Google Docs) each procedure included in your study.

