- The TST will be applied during brain states reflecting strong corticospinal recruitment, brain states reflecting weak corticospinal recruitment, and randomly selected brain states according to an established procedure (Magistris et al. 1998), with details below. EMG data will be recorded and processed offline to calculate the primary and secondary outcomes. EEG data will be recorded and processed offline to ensure accurate state identification as a quality control procedure (Zrenner et al. 2018; [name] et al. 2020).
 - TMS will be timed using the real-time EEG analysis algorithm
 - After an interstimulus interval equal to delay 1, Wrist PNS will be applied.
 - After an interstimulus interval equal to delay 2, Erb's point PNS will be applied.
- The EEG cap, EMG electrodes, and PNS electrodes will be removed and participants will leave the laboratory.
- If participants are asked to complete two sessions, the same experimental procedures described above may be used during the second session. The second session may be used to evaluate between-day reliability of the measurements made during the first session. At least 24 hours will elapse between sessions.

Experiment 3

Days 1-4 (at least 24 hours will elapse between sessions)

- The participant and research team member will review and discuss the informed consent document.
- Eligibility will be formally determined by the research team member by reviewing a list of the inclusion and exclusion criteria verbally with the participant (see attachments).
- Participants will complete a short demographics survey.
- The skin on the left hand and wrist will be cleaned using isopropyl alcohol. EMG electrodes will be attached to a maximum of 5 hand and wrist muscles using medical grade adhesive. PNS electrodes will be attached to the left wrist using medical grade adhesive. A ground electrode will also attached to the dorsum of the hand in the same manner.
- The scalp TMS hotspot will be determined as the site of the scalp producing the most reliable focal muscle twitch within the left first dorsal interosseous muscle. The scalp RMT will be determined using an automatic threshold tracking tool (Awiszus and Borckhardt 2011) as the minimum stimulation intensity needed to elicit a MEP of 50 microvolts in peak-to-peak amplitude in response to 50% of stimuli. EMG signals may be recorded for offline quality control analysis.

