- Single-pulse TMS pulses will be delivered during EEG and EMG recordings. Immediately afterwards, EEG and EMG data will be analyzed using machine learning. The brain states identified using machine learning will be used for subsequent real-time EEG analysis.
- The M-max following PNS at the wrist will be determined by increasing stimulation intensity until a larger response cannot be obtained. EMG signals may be recorded for offline quality control analysis.
- Electrode positions may be marked on the skin using a skin-safe surgical marker to ensure consistent electrode placement across sessions.
- Single-pulse TMS to the scalp and wrist PNS will be performed to calculate delays needed for PCMS (see Design and Methodology). EMG signals will be recorded to enable delay calculation.
- Delays for PCMS application will be calculated using the following formulas (units are milliseconds; Bunday and Perez 2012; Urbin et al. 2021):
 - Peripheral Conduction Time (PCT) = (F-wave latency –M-wave latency) * 0.5
 - Central Conduction Time (CCT) = MEP latency (PCT + M-wave latency)
 - Active PCMS Delay = (PCT CCT) X ms (where X = 1 5 ms)
 - \circ Control PCMS Delay = (PCT CCT) + X ms (where X = 5 30 ms)
- The real-time EEG analysis algorithm will be used to deliver TMS pulses during the target brain state for that session. The order of brain states targeted per session will be counterbalanced across subjects. During this time, participants will rest quietly with their eyes open (Zrenner et al. 2018; [name] et al. 2020). EEG and EMG data will be recorded for offline quality control analysis.

- Participants will complete pre-PCMS measurements of corticospinal excitability, spinal excitability, voluntary motor output, and manual dexterity (see Design and Methodology). EMG signals will be recorded during all measurements and processed offline to obtain outcome measures. EEG may recorded for offline quality control analysis.
- The PCMS intervention will be delivered (see Design and Methodology) during the target brain state for that session. The order of brain states targeted per session will be counterbalanced across subjects. EEG and EMG signals will be recorded for subsequent quality control analysis.
 - Active PCMS during brain states reflecting strong corticospinal recruitment, with the delay between scalp TMS and wrist PNS equal to the Active PCMS delay.

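### Experiment 3 counterbalances session order but leaves session out of the model, which costs power under a trend and lets incomplete participation shift the condition main effects

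*Combined protocol and SAP*

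**What the plan says.** Section 4 describes Experiment 3 as "within-subjects, single group", with four PCMS conditions, each given in its own session. The session allowance is "Up to 4 sessions for <= 6 hours each". After technical difficulties, "<= 3 additional sessions may be requested, during which any combination of the procedures described below may be applied". Section 11 sets the spacing: "Days 1-4 (at least 24 hours will elapse between sessions".

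Order is controlled by design. Section 4 states "The order of conditions will be counterbalanced", and section 11 repeats it: "The order of brain states targeted per session will be counterbalanced across subjects". Neither section names the scheme or the number of sequences. Section 4 also says "Participants may complete one, two, three or four of the conditions".

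Every session has its own measurements just before PCMS and at 0, 20 and 40 minutes after. Section 5 analyses all Experiment 3 outcomes with linear mixed models: "fixed effects of condition and time point, random intercept of subject". Main effects are tested by likelihood ratio, and post-hoc contrasts are corrected for multiplicity. The plan mentions no session, sequence, preceding-condition or condition-by-time term, and no comparison of baselines across sessions.

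**The concern.** Counterbalancing concedes that order may matter, but the analysis does not use the order that the design controls. The primary and secondary outcomes are repeated performance tasks. With up to 5 maximal contractions and 5 peg-test attempts at each of 4 times over 4 sessions, a participant can make 5 × 4 × 4 = 80 attempts at each task, so a trend over sessions is plausible.

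Two things are at stake. With complete, balanced data an unmodelled trend becomes residual variance, and the trial loses power that it could keep. With incomplete participation, which the protocol allows, conditions no longer fall equally often in early and late sessions, and part of the trend can pass into the condition main effects.

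Carry-over is a separate matter. Outcomes stop at 40 minutes, so the trial has no later measurement within a session. The next session's baseline is the only data on residual effects, and the plan does not use it for that.

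**Working it through.** **Plan's own figure.** Section 15 raises N from 14 to 20 without an effect size, SD, correlation or power, so there is no power figure to reproduce. The inputs from the documents are N=20, up to four sessions, four time points per session, alpha 0.05 and the section 5 model. Effect sizes, trends, variances and completion patterns below are assumptions.

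**1. Complete data on a balanced square, one score per session.** Each condition falls equally often in each session position, so a linear trend adds the same amount to every condition mean and the bias is 0. The trend goes into the residual:
- Centred session numbers are −1.5, −0.5, 0.5 and 1.5, with sum of squares 5. Over 20 participants this is 100, so slope b (in residual SD) adds 100b² to the residual sum of squares.
- Residual df without a session term: 80 − 1 − 19 − 3 = 57. With it: 54.
- Residual mean square is inflated by 1 + 100b²/57, that is 1.11 at b=0.25 and 1.44 at b=0.5. The estimated standard error rises by factors of 1.053 and 1.199.
- Take an effect of 0.9 residual SD. Its true standard error is √(2/20) = 0.316, so the signal is 0.9/0.316 = 2.846. The critical value at 57 df is 2.002.
- Power ≈ Φ(2.846 − 2.002 × factor): 0.80 at b=0, 0.77 at b=0.25 and 0.67 at b=0.5.

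Repeated simulation agrees. The incomplete columns assume that 30% of participants complete two sessions, 30% three and 40% four.

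| Trend per session | Complete, no term | Complete, with term | Incomplete, no term | Incomplete, with term |
|---|---|---|---|---|
| 0 | 80-81% | 80-81% | 62-65% | 61-64% |
| 0.25 SD | 76-78% | 79-81% | 60-62% | 62-64% |
| 0.5 SD | 66-67% | 79-80% | 50-52% | 61-62% |

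Most of the fall from 80% in the incomplete columns comes from having fewer sessions. The part due to omitting the term is the gap between the last two columns.

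**2. Incomplete data, model as written (four time points per session).** If two of the four sequences of a Williams square (each condition follows each other one equally often) stop after session 2, one unit of trend per session shifts the weak, random and control contrasts against strong-state PCMS by +0.37, −0.40 and −1.34 units. Which sequences stop decides the sign and size. With session in the model all three shifts are 0. If each participant completes one to four sessions at random, the shift averages 0 over trials, but within a single trial it has an SD of about 0.37 to 0.45 units.

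Type I error of the condition test (400 simulated trials per setting, Monte Carlo error about 0.01 to 0.02; residual SD 0.3, no random session-to-session variation):

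| Practice per session | Complete, no term | Complete, with term | Incomplete, no term | Incomplete, with term |
|---|---|---|---|---|
| 0 | 0.045 | 0.045 | 0.07 | 0.0625 |
| 0.1 | 0.03 | 0.0575 | 0.13 | 0.07 |
| 0.2 | 0.0125 | 0.055 | 0.21 | 0.055 |

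These are steep trends. A session mean of four values has SD 0.3/√4 = 0.15, so 0.1 and 0.2 are 0.67 and 1.33 of that SD.

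**3. Condition-by-(post versus pre) contrast.** A trend between sessions moves the baseline and the post values of a session together. In the same incomplete patterns the shift in this contrast is 0 without any session term. The exposure in step 2 therefore arises because section 5 tests main effects, which average the pre-PCMS values into the condition effect.

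**4. Carry-over.** Equal carry-over after every condition cancels in a complete balanced scheme. Suppose 1 unit remains after strong-state PCMS only. In a Williams square each other condition follows it in 1 of 4 sequences, so every contrast with strong-state PCMS shifts by 0.25. In a cyclic square one condition follows it in 3 of 4, so that contrast shifts by 0.75 and the others by 0. The session term leaves these values unchanged.

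**5. Cost of the term.** Variance inflation of the condition contrasts is 1.00 with complete data. With one to four sessions at random the median is 1.05 and the 95th percentile 1.16.

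**The case against.** The strongest reply is that the design already deals with order: it is counterbalanced and each session has a fresh baseline. Much of this stands. A reader might infer that practice and residual effects generally enter the condition contrasts. The documents do not support that. Under complete balance a trend only adds error and makes the test conservative, and equal carry-over cancels. Hypothesis 3 concerns an increase after PCMS, and a contrast of within-session change would be immune to a between-session trend. However, section 5 names main effects and no condition-by-time term, so as written that protection is not used.

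A reader might also infer that 24 hours is too short. That is not shown. It is a minimum, and nothing in the documents says how long PCMS effects last beyond 40 minutes. A positive residual after strong-state PCMS alone would favour the comparators, against the trial's hypothesis.

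A third objection is that a baseline check at N=20 is weak, and this is correct. Under an assumed carry-over of 0.5 SD after strong-state PCMS only, a 3-df test has about 21% power with complete data and 12% with the 30/30/40 completion pattern. At 1 SD the figures are 70% and 37%. A significance pre-test should not decide what is reported.

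Finally, the protocol permits incomplete participation but does not predict it, so the size of the bias in practice is unknown.

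**Conclusion.** The point holds as a recommended improvement to the analysis. With complete, balanced data the omission costs power only: about 2 to 4 percentage points at a trend of 0.25 residual SD per session and about 13 at 0.5, from 80%. With incomplete participation a trend can shift the condition main effects in a given trial and raise type I error, to 0.13 and 0.21 under the two steep trends simulated. A session term largely restores it.

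All sizes depend on assumed trends, variances and completion patterns. The type I figures also assume no random session-to-session variation. With such variation at SD 0.2, complete data and no practice, type I error is about 0.3 with or without the term, because the model has only a participant intercept. That is a separate weakness which a session fixed effect does not cure.

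No conclusion is drawn that carry-over exists or that the interval between sessions is wrong.

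**What to change.** Add session number as a categorical fixed effect to every Experiment 3 model, numbering any repeat session by its actual order. Name the counterbalancing scheme.

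Separately, report in all cases the pre-PCMS baselines by preceding condition, as estimates with confidence intervals, and a sensitivity analysis with preceding condition as a covariate. Neither should depend on a significance pre-test. The interval between sessions need not change on this account.

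The cost is analysis-plan wording, plus a record of each session's order. The term uses three degrees of freedom, or more if additional sessions occur (up to seven sessions, hence six). It costs nothing in contrast variance when data are complete and balanced, and roughly 5% when they are not. If there is no trend, the loss of power is at most about 2 points. The baseline report will be imprecise at N=20 and should be described as such.

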EEG: EEG poses no known medical risk. Participants may experience scalp discomfort during application of the EEG electrodes. Participants may be annoyed by any remaining gel in their hair after completion of EEG procedures.

EMG: EMG poses no known medical risk. Participants may experience a mild itching sensation or skin irritation from the adhesives used to attach the EMG electrodes.

TMS: TMS, when applied in individuals without any contraindications (see exclusion critieria), and at a rate <= 1 Hz (as applied in this protocol) is considered to be minimal risk by the international neurophysiology community (Rossi et al. 2020) and the National Institutes of Health. Participants may experience mild muscle contractions (scalp, back, face, arms/hands) during TMS and may find it uncomfortable, but it is not painful. Some participants experience a mild headache after TMS.

PNS: PNS, when applied in individuals without any contraindications (see exclusion criteria), poses no known medical risk but can be painful. Participants may experience a burning or stinging sensation during PNS, and/or mild itching or skin irritation from the adhesives used to attach the EMG electrodes.

Behavioral testing: The behavioral testing procedures used here, including maximum voluntary contractions and manual dexterity assessment via the 9-hole Pegboard Test, pose no known medical risk. Participants may experience mild hand muscle soreness or fatigue during or after the behavioral assessments.

There is a risk of loss of confidentiality.

41 Describe how each risk is mitigated/minimized.

To input text, click in the light grey area below.

EEG: The risk of scalp discomfort will be minimized as much as possible by taking care to ensure subject comfort during EEG set-up and communicating with the participant continuously regarding their comfort level. Medical grade supplies will be used at all times.

EMG: Medical grade adhesives will be used at all times to minimize skin irritation and itching.

TMS: Participants will be fitted with earplugs during all TMS procedures to protect hearing. If a participant finds TMS too uncomfortable, they may choose not to continue participation.

PNS: Medical grade adhesives will be used at all times to minimize skin irritation and itching. The lowest possible stimulation intensities will be used to reduce pain experienced during PNS. If a participant finds PNS too uncomfortable, they may choose not to continue participation.

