Behavioral testing: To minimize the risk of fatigue and soreness, participants will receive breaks during behavioral testing.

Loss of confidentiality: We will take all steps to minimize loss of confidentiality, including storing all studyrelated documents on password protected computers and in locked file cabinets behind locked laboratory doors of 546F BEL. Only study personnel will have access to personally-identifiable information.

Data Safety Monitoring

For additional information regarding data safety monitoring boards and data safety monitoring plans, please see Section 21 of our Policies and Procedures.

Click on the check box (or double click and type an "X" if using Google Docs).

- **42** This study is minimal risk and does not require a Data Safety Monitoring Plan (DSMP) or a Data Safety Monitoring Board (DMSB).
- 43 X This study does not have a Data Safety Monitoring Board, but researchers have an internal plan/policy to monitor for safety. Complete Data Safety Monitoring Details (44-51).

44 This study has a Data Safety Monitoring Board (DSMB). Complete Data Safety Monitoring Details (44-51) or upload this study's Data Safety Monitoring Board's charter.

Data Safety Monitoring (Details)

45 How is safety information collected?

To input text, click in the light grey area below.

Safety information will be collected weekly as part of research team meetings. Researchers working on this study will provide a verbal report of any and all safety issues encountered during study sessions. If a safety issue is encountered, the PI will create a brief written description of the encountered issue and the steps taken to resolve this issue. Additional monitoring will be conducted by an independent medical monitor, please see Data Safety and Monitoring Plan (attached).

46 When will safety data collection start (for each participant or for the whole study, as applicable)?

To input text, click in the light grey area below.

For each participant, safety data collection will begin immediately after informed consent is provided and will continue until each participant completes their participation in the study.

47 How frequently will safety data be collected?

To input text, click in the light grey area below.

Safety data will be collected during every experimental session if a safety issue arises. Safety data will be verbally reported and discussed during weekly research team meetings.

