48 Who will review the data for safety? To input text, click in the light grey area below.

The PI will review the data for safety.

How frequently will data be monitored for safety concerns?
To input text, click in the light grey area below. Data will be monitored for safety concerns weekly at research team meetings.

50 What data will be reviewed? To input text, click in the light grey area below. Verbal reports of research team members

51 State the frequency or periodicity of the review of cumulative data?

To input text, click in the light grey area below. We will review the safety data at the time of continuing IRB review as well as at the time of NIH progress reporting.

52 State any conditions that would trigger an immediate suspension of the research. To input text, click in the light grey area below.

If a serious adverse event occurs, enrollment and procedures will be suspended until a review can be performed by the IRB and until the IMM provides approval to re-start the study. Depending on the results of consultation with the IRB and IMM, the procedure associated with the serious adverse event may be removed from the project (after obtaining IRB approval) or specific language may be added to the written informed consent document to reflect any changes in risk level.

Early Withdrawal

Only complete this section if there are planned conditions under which a participant will be withdrawn from the study. *If not applicable, skip to 56.*

Include this information in your consent form.

53 List the criteria for withdrawing individual participants from the study (e.g., safety or toxicity concerns, emotional distress, inability to comply with the protocol, or requirements from study sponsor). To input text, click in the light grey area below.

n/a

54 Describe any necessary procedures for ensuring the safety of a participant who has withdrawn early.

To input text, click in the light grey area below. n/a

55 Describe any pre-specified criteria for stopping or changing the study protocol due to safety concerns.

To input text, click in the light grey area below. n/a

REQUIRED DISCLOSURES

Required Consent Disclosures

Identify each element below that may require additional information to be disclosed in the consent form.

Click on the check box (or double click and type an "X" if using Google Docs).

- **56** It is reasonable that researchers could discover or suspect child or elder abuse.

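### Safety data are collected only when an issue arises, and no procedure list contains a symptom question, although the protocol expects after-effects; a short fixed symptom check would be better (minor).

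*Combined protocol and SAP*

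**What the plan says.** All references are to the combined protocol and SAP.

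- **Item 47** (frequency of collection): "Safety data will be collected during every experimental session if a safety issue arises".
- **Item 45** (method): at weekly team meetings, staff give a "verbal report of any and all safety issues encountered during study sessions". The PI writes a brief note if an issue has been met. The item adds: "Additional monitoring will be conducted by an independent medical monitor, please see Data Safety and Monitoring Plan (attached".
- **Item 46** (window): collection starts at consent and "will continue until each participant completes their participation in the study". No question, form or contact is named.
- **Items 49 and 50** (review): "Data will be monitored for safety concerns weekly at research team meetings"; the data reviewed are the team's verbal reports.
- **Item 52**: "If a serious adverse event occurs, enrollment and procedures will be suspended", pending IRB review and the medical monitor's approval to restart.
- **Item 40** (expected effects): "Some participants experience a mild headache after TMS". For behavioral testing: "Participants may experience mild hand muscle soreness or fatigue during or after the behavioral assessments".
- **Section 13e**: a past adverse reaction to TMS or PNS is an exclusion.
- **Section 11**: in each experiment, the only required step between the last stimulation or measurement and departure is removal of the recording and stimulating equipment.

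**The concern.** As written, collection is passive. A record depends on an issue coming to a staff member's notice, and item 45 ties that to the session itself. Two of the effects that item 40 anticipates can begin after stimulation or testing has finished, possibly after the participant has left. Without a fixed question, an empty record does not distinguish a participant with no symptom from one who was not asked.

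This has some practical weight because participants return. Sessions may be as little as 24 hours apart, and a previous adverse reaction to TMS or PNS is an exclusion. A reaction to one session is therefore relevant to whether the next should go ahead. At stake are the completeness of the non-serious safety record and knowledge of earlier reactions before repeat stimulation. Efficacy results are not at stake.

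**Working it through.** The plan gives no safety figure to reproduce, so the check sets its sections side by side and then counts the occasions concerned.

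**1. What triggers a record.** Item 47 makes it conditional on an issue. Items 45 and 50 make the source a staff verbal report. Item 46 gives an unconditional window but no method. No unconditional collection step appears elsewhere in the text.

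**2. How each kind of effect would reach the record.**

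- *Noticed during the session.* Covered by item 45. In Experiment 3, participants also stay for measurements at 0, 20 and 40 minutes after PCMS, which gives staff time to notice or be told.
- *Present at the end of the session but not mentioned.* No listed step asks. Item 41 describes continuous communication about comfort for EEG only. For TMS and PNS it says that a participant who is too uncomfortable may stop.
- *Beginning after departure, with another session to come.* Two routes exist: the participant volunteers it, or a repeated eligibility review brings it out. In Experiment 3 that review is listed under Days 1-4, so it may recur at each session. In Experiments 1 and 2, Section 4 says that each session involves the same experimental procedures, while Section 11 says only that they may be used again, so repetition is possible but not certain. The review asks about history of adverse reactions and does not ask about the effects in item 40. A participant might not count a mild headache as an adverse reaction.
- *Beginning after the last session.* Outside the item 46 window once participation is complete, and not pursued here.

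**3. Number of occasions.** Intervals between sessions = sessions − 1.

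- Experiments 1 and 2: 2 − 1 = 1 per participation; 3 − 1 = 2 with the optional third session.
- Experiment 3: 4 − 1 = 3 per participation; 7 − 1 = 6 with the three optional extra sessions.

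At the target N = 20 per experiment (Section 14), assuming that all planned sessions are completed:

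- Session ends: 20 × 2 + 20 × 2 + 20 × 4 = 160.
- Intervals between sessions: 20 × 1 + 20 × 1 + 20 × 3 = 100.

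These are occasions on which the protocol text lists no explicit symptom question. They are not counts of missed effects.

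**The case against.** The strongest objection is that item 45 hands part of the monitoring to an attached Data Safety and Monitoring Plan that is not among the documents. That would be the natural place for a symptom form, and the eligibility checklist is also an attachment. A reader might infer that the study has no symptom check at all. The documents do not support this. They show only that items 45 to 47 and the procedure lists do not describe one. This part of the objection stands and limits the conclusion.

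Item 47 also answers a form prompt in one awkward sentence. It can be read as collection in every session whenever there is something to record, and item 45 does not forbid staff from asking. This stands in part: asking is allowed, but nothing requires it.

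The Experiment 3 eligibility review and the 40-minute period after PCMS are real mitigations. They narrow the gap without replacing a symptom question.

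Two further inferences should be resisted. One is that after-effects are probably under-recorded: there is no event or reporting rate behind that claim. The other is that weekly review combined with a 24-hour minimum interval lets reactions go unnoticed before the next session. Actual spacing is not given, staff may tell the PI at any time, and meeting timing says nothing about whether a symptom was asked about.

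**Conclusion.** The point holds as a minor one, limited to non-serious effects and to the protocol text available. The collection rule is conditional and its source is staff report. The procedure lists contain no symptom question, while item 40 expects effects that can begin late. Such effects may go unrecorded unless they are volunteered or brought out by a repeated eligibility review.

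The extent is up to 160 session ends and 100 intervals between sessions at target enrolment, assuming full attendance. The number of unrecorded effects is unknown.

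A reader might take this to mean that serious events are poorly handled or that the trial's results are affected. Neither follows: item 52 provides for suspension after a serious event, and no endpoint, analysis or sample size depends on this rule. If the attached plan already has a symptom check, what remains is an inconsistency in wording.

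**What to change.** Replace the conditional wording in item 47 with a short fixed symptom question covering the item 40 effects, plus an open field for anything else. Ask it at the end of every session and before stimulation at every later session. Report any unexpected reaction to the PI before further stimulation. Add the question to the three procedure lists in Section 11. If the attached Data Safety and Monitoring Plan already contains such a check, align items 45 to 47 with it instead.

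**Cost.** For n sessions, checks = n + (n − 1) = 2n − 1. Assuming 2 to 3 minutes per check:

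- Two sessions: 3 checks, or 6 to 9 minutes against up to 2 × 6 = 12 hours.
- Four sessions: 7 checks, or 14 to 21 minutes against up to 4 × 6 = 24 hours.
- Whole study at target enrolment: 160 + 100 = 260 checks.

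More mild events will be recorded, and a session may occasionally be delayed. In a within-subject design, a delayed session that is never rescheduled would leave a condition missing, so it should be rebooked where possible. Stimulation, endpoints and sample size do not change.
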